This is the second phase of a multi-center trial of ACS patients. The first phase was a safety study involving 31 patients and was completed in December 2012. US Food and Drug Administration (FDA) reviewed the safety and efficacy data from the first phase and approved proceeding to this phase. In this trial, 128 participants will be randomized in a 1:1 ratio to either initial LDL-apheresis and an oral daily dose of 40-80mg of Atorvastatin or equivalent (ILLT group) vs. a daily dose of 40-80mg of Atorvastatin or equivalent without LDL-apheresis (SMT group) following an uncomplicated PCI. Intravascular ultrasound with virtual histology (IVUS-VH) derived coronary atheroma volume and composition will be obtained at baseline and 90 days after enrollment, while peripheral blood sampling will be performed at enrollment, and at 24 hours, 30 days, and 90 days post-PCI, along with a four-month and a six-month clinical follow-up visits to determine whether the ILLT group will affect:

1. The total number of and percentage of patients with major peri-PCI procedure adverse events (primary safety endpoint)

2. The total number of and percentage of patients with statin-related abnormal liver function test events and statin-related muscle injury events (secondary safety endpoint)
3. The total atheroma volume within a ≥ 20 mm long segment of the target coronary artery at 90 days IVUS-VH follow-up (primary effectiveness endpoint)
4. The %NC component within a ≥ 20 mm long segment of the target coronary artery at 90 days IVUS-VH follow-up (secondary effectiveness endpoint)
5. The EPC-CFU/ml of peripheral blood, compared to SMT group from baseline to 30 days and 90 days post-PCI (secondary effectiveness endpoint)
6. The major adverse CV events (MACE) at 90 days and at six months follow-up (secondary effectiveness endpoint)

2. Background and Significance

2(a) Background

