The safety objective of this study is to collect additional safety data for ACS patients who undergo the LDL-apheresis post-PCI procedure and the use of maximum dose of statin drugs.

The primary effectiveness objective of this study is to compare the total atheroma volume within a ≥ 20 mm long segment of the target coronary artery in ACS patients with an uncomplicated PCI randomly assigned to LDL-apheresis with 40-80mg daily of Atorvastatin or equivalent (ILLT group) or 40-80mg daily of Atorvastatin or equivalent only (SMT group). The specific hypothesis being tested is: ILLT is superior to SMT in reducing the total atheroma volume at 90 days IVUS-VH follow up.

The secondary effectiveness objectives of this study will be: (1) to compare %NC component of atheroma within a ≥ 20 mm long segment of the target coronary artery; (2) to compare the EPC-CFU/ml of peripheral blood in the two treatment groups; and (3) to compare MACE, associated with the two treatment groups at 90 days and at 6 month follow-up.

Rationale for study effectiveness objectives: The rationale for the study effectiveness objectives includes the observation of increased recurrent CV events in ACS patients early (three months) post-index event, despite intensive statin pharmacotherapy, due to progression and rupture of non-critical coronary lesions. Aggressive LDL lowering using LDL-apheresis (ILLT) as proposed in this study will test a novel strategy of non-critical coronary atheroma regression at 90 days, and hence reduce early (12-week) MACE events in ACS patients, sustained at end of study (at least six months follow-up). We also propose to test whether EPC mobilization with aggressive LDL lowering correlates with coronary atheroma regression, change in atheroma composition (%NC), and MACE events. We acknowledge that the scope of this study does not test the mechanism of EPC targeting to site of coronary VP and its endothelialization, however, it would provide for the first time important initial evidence which could be tested in future dedicated studies.

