Peripheral blood sampling for EPC quantification will be performed using cell culture only at VA North Texas center in Dallas. This will ensure an optimal number (at least 50) uniformly standardized and cost-effective EPC cell culture assays in this multi-center study. A limited number (n=25) of FACS EPC analysis will be performed to correlate cell culture and FACS levels of circulating EPC. Such a correlation would be important to demonstrate if future large-scale use of this treatment strategy of EPC mobilization is to be implemented with the rapid and less cumbersome FACS instead of the established standard of EPC cell culture technique. Approximately 10ml of whole blood is needed for either assay. Cell culture assay based upon our published methodology¹¹ will be performed ≤ 48 hours of collection. EPC flow cytometry will be performed using standard methodology³⁴. All EPC sampling schedules are indicated in **Figure 8** and in **Table 1**, along with all other scheduled clinical and laboratory tests. All EPC analyses will be compared to baseline pre-PCI levels. **Table 1** summarizes all planned follow-up visits and tests.

Follow-up tests like fasting lipid (FL) will be performed immediately following LDL-apheresis in ILLT device group at about 12-24 hours post-PCI procedure. The same fasting lipid profile test for SMT control group will be done at 24 hours post-PCI procedure or prior to hospital discharge, whichever comes earlier. A post-PCI 30-day visit will include a complete blood count (CBC) and basic metabolic profile (BMP) with LFT. The 30-day post-PCI CBC, BMP and LFT are clinically indicated tests. A 30- and 90-day FL in both treatment groups, along with EPC assay and an additional 60 day phone follow-up, will ensure strict lipid management and close follow-up for clinical

events, and prevent any loss of recruited study subjects. After the 90-day follow-up cardiac catheterization and IVUS-VH analysis, all study subjects will return in 30 days for a 4-month study visit with CBC, BMP, LFT and FL. After an additional 60 days, or at 6 months from index PCI, all patients will return for a study completion visit and a FL assay. Any MACE will also be collected via searching the Austin database of VA hospital utilization by Hines CSPCC staff. This dual MACE assessment will help avoid missing out on any participating site MACE.

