- (2). The EPC-CFU/ml of peripheral blood assessed at various time points (pre-PCI, post-PCI, 30 days of follow-up, and 90 days of follow-up) will be analyzed via Mixed Linear models with random intercepts. The treatment effect, time effect and their interaction will be considered with or without

adjusting for age, pre-existing CAD, pre-existing diabetes, baseline LDL levels, and other relevant covariates such as ACS, peripheral vascular disease, and chronic kidney disease. The statistical test of interest is the time by treatment interaction.

- (3). Contrasts will be used in the Mixed Linear models to compare the differences among any specifically interested time points.

4(g)(vi). Statistical Analysis of Safety Endpoints and Complications: The primary safety endpoints, the secondary safety endpoints, and the incidence of major adverse cardiovascular endpoints (MACE) including death, myocardial infarction, coronary revascularization, and stroke will be analyzed in two ways. For each type of event, the percentage of people who experience the event at least once will be compared using the chi-square test. Logistic regression models will be performed to adjust for the covariates such as age, pre-existing CAD, and pre-existing diabetes. In addition, a similar analysis will be done for all AE and SAE that are possibly or probably attributable to the study intervention.

An event-based analysis will also be done since adverse events can be recurrent. In this analysis, a non-parametric method called the mean cumulative function (MCF)^{35,36} will be used as an alternative to the above crude incidence rate analyses. The overall safety profiles as well as the safety profiles in specific subgroups over the whole study period will be compared for the two randomization groups including the times of event recurrence and censoring mechanisms.

Time to event (survival analysis) will also compare the time to first MACE between treatment groups. A second survival analysis will be performed to identify risk predictors and to evaluate whether the observed treatment effect is modified by adjusting for covariates such as pre-existing CAD and pre-existing diabetes.

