## **Secondary Effectiveness Outcome Measures**

The secondary effectiveness outcome measures will include:

1. The %NC component of atheroma. The %NC component of atheroma will be obtained via IVUS-VH at 2 time points (baseline during index PCI and 90-day follow-up).
2. EPC-CFU/ml of peripheral blood. The cell culture assay and quantification of circulating EPC-CFU will be performed for patients recruited at the Dallas VA center only. The assay will be done at 4 time points (pre-PCI, post-PCI, 30-day follow-up, and 90-day follow-up).

3. The major adverse cardiovascular endpoints (MACE) including death, myocardial infarction, coronary revascularization, and stroke during the follow-up periods. The major adverse CV events will be collected via both clinical visits for up to 6 months post-PCI and searches of the VA Austin database for up to 1 year post-PCI. Approvals for using the patients' Social Security Numbers for data searching will be obtained via informed consent form.

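### The named EPC test spans all four visits and can be significant on the 24-hour sample alone, so it does not specifically test the 30- and 90-day objective

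*Protocol*

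**What the plan says.** Protocol 1(c) item 5 states the EPC objective with time points: "The EPC-CFU/ml of peripheral blood, compared to SMT group from baseline to 30 days and 90 days post-PCI". Section 4(a) states it without any: "to compare the EPC-CFU/ml of peripheral blood in the two treatment groups". On sampling, 1(c) says "peripheral blood sampling will be performed at enrollment, and at 24 hours, 30 days, and 90 days post-PCI".

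Protocol 4(g)(v)(2) fits a random-intercept mixed linear model to the pre-PCI, post-PCI, 30-day and 90-day values and adds: "The statistical test of interest is the time by treatment interaction". The SAP (Analysis of Secondary Effectiveness Outcomes) says the same. Both then allow contrasts between time points of interest, without naming the time points, the number of contrasts or their rank against the interaction. Section 4(e) says that EPC results are compared with pre-PCI levels. Section 4(g)(ix) sets two-sided 0.05 throughout, with no adjustment across secondary endpoints.

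**The concern.** The objective concerns two later visits, while the named test concerns any departure from parallel profiles over four. A significant interaction does not say where the groups differ. It could come wholly from the sample taken about a day after PCI, when only the ILLT arm has apheresis scheduled around the same time. A reader who takes the named test as the answer to item 5 would then credit ILLT with a 30- and 90-day effect that the data do not show. The contrasts could correct this, but nothing obliges the analyst to run the 30- and 90-day ones or to put them first.

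**Working it through.** **No EPC figure to reproduce.** The only sample-size figure is for the primary endpoint. A t-test with d = 0.65 and 90% power needs 51 per arm; 102/0.8 = 127.5, so 128. That agrees with the plan but says nothing about EPC.

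**Inputs from the documents.** Four visits; two-sided alpha 0.05; EPC culture at Dallas only. Dallas numbers: 128/4 = 32, or 1.5 per month × 22 months = 33, so about 16 per arm. Section 4(e) mentions at least 50 assays; read as patients, that is 25 per arm.

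**Assumptions.** The documents give no EPC variance, correlation or 24-hour effect. I take SD 1 at each visit, correlation ρ = 0.5, complete data and categorical time. Effects e are in SD units.

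**Step 1: interaction test under a 24-hour-only difference.** With δ the vector of group differences by visit and within-patient variance 1 − ρ = 0.5, the noncentrality is

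λ = (n/2) × Σ(δₜ − δ̄)² / 0.5, on 3 and 3(2n − 2) df.

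For δ = (0, e, 0, 0), Σ(δₜ − δ̄)² = 0.75e², so λ = 0.75ne².

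| n per arm | e | λ | Rejection |
|---|---|---|---|
| 16 | 0.3 | 1.08 | 12% |
| 16 | 0.5 | 3.00 | 26% |
| 16 | 0.8 | 7.68 | 61% |
| 25 | 0.5 | 4.69 | 40% |
| 25 | 0.8 | 12.00 | 82% (simulated; 83% by formula) |

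A larger EPC sample raises these rates.

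**Step 2: a test confined to 30 and 90 days.** Its δ is (0, 0) under the same scenario, so λ = 0 and it rejects at 5%, with or without adjustment for the pre-PCI count.

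**Step 3: power when the effect is where the objective places it.** After adjustment for the pre-PCI count, the 30- and 90-day values have variance 1 − 0.25 = 0.75 and covariance 0.5 − 0.25 = 0.25. The joint test has λ = (n/2) δ′Σ⁻¹δ on 2 df. At 16 per arm and 0.8 SD, for both visits, λ = 8 × 0.64 × 2 = 10.24; for 90 days only, λ = 8 × 0.64 × 1.5 = 7.68. Simulated power, good to about one percentage point:

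| True effect at | Planned interaction | Adjusted joint 2-df | Adjusted 30/90 average, 1-df |
|---|---|---|---|
| 30 and 90 days | 74% | 76% | 86% |
| 24 h, 30 and 90 days | 62% | 77% | 86% |
| 90 days only | 61% | 63% | 33% |

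**Step 4: what the adjustment contributes.** Without the baseline adjustment, restricting the test to 30 and 90 days gains no power. At 25 per arm with a difference of 1.0 within-patient SD at both visits, the interaction has 84.6%, the unadjusted 1-df contrast 81.8% and the unadjusted 2-df contrast 72.7%.

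**Step 5: if time were linear.** At 25 per arm, a 24-hour-only difference of 1.0 within-patient SD still rejects in 29% of trials (time in days) or 12% (visit number). Categorical coding gives 71.8%.

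**The case against.** The interaction contains the baseline-to-30 and baseline-to-90 differences and has reasonable power for them. Item 5, the pre-PCI reference in 4(e) and the contrasts sentence together point to the two natural contrasts. The 24-hour sample also has a purpose: the scientific premise in 3(a) is failed early mobilization after PCI in ACS, and 4(a) names no time point. All of that stands. It makes the gap small and easily closed. It does not close it, because the plan still names the interaction as the test of interest and leaves the contrasts unnamed and unranked.

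Several stronger readings are tempting and are not supported:

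- *The plan does not test its objective at all.* It does respond to 30- and 90-day effects; it does not test them specifically.
- *The interaction wastes power.* Step 4 shows that the gain comes from using the pre-PCI count, not from dropping the 24-hour visit.
- *A transient change will be reported as sustained mobilization.* No document states an objective in those words, and how the result would be reported is conjecture.
- *The 24-hour EPC sample falls before apheresis in some ILLT patients and after it in others.* The supporting words, "immediately following LDL-apheresis in ILLT device group at about 12-24 hours post-PCI procedure", describe the fasting lipid draw. Table 1 lists lipids and EPC on the same post-PCI row, so a mix is possible but only inferred.

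**Conclusion.** The point holds in limited form: the named EPC test is wider than the objective in 1(c) item 5 and can be significant with no difference at 30 or 90 days. The rejection rates of 26–61% at 16 per arm and 40–82% at 25 per arm rest on assumed SD, correlation, a 24-hour shift of 0.5 to 0.8 SD, and categorical time. At 0.3 SD and 16 per arm the rate is only 12%. The direction does not depend on these values; the size does. EPC is a single-site secondary endpoint with no power calculation of its own, and the primary conclusion is unaffected.

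**What to change.** In Protocol 4(g)(v)(2) and the matching SAP paragraph, make the test of interest the ILLT–SMT differences in EPC-CFU/ml at 30 and 90 days, adjusted for the pre-PCI count (or fitted with a common baseline mean) and tested jointly on 2 df. Follow it with each visit separately. Keep the 24-hour comparison as supportive.

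Do not rest the test on the 30/90-day average alone. It does best when both visits share the effect, but falls to about 33% against 61% for the interaction when only one visit does (16 per arm, 0.8 SD).

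The cost is wording: no added patients, visits or assays. The downside is that the 24-hour difference leaves the named test.

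Two minor clarifications can go in at the same time. Fix one covariate set, replacing ACS, which every patient has by eligibility, with unstable angina versus non-ST-elevation MI as in 4(g)(viii). Also record whether the post-PCI EPC sample was drawn before or after apheresis.

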ACS is defined as chest discomfort lasting at least 10 min within the last 24h, new ≥ 1 mm ST-wave or dynamic T-wave changes in at least two contiguous EKG leads but without significant ST elevation, and/or troponin I or T levels above the 99th percentile. Abnormal LFT is defined as any liver transaminases (ALT or AST) ≥ 3 times the upper limit of the normal laboratory reference. Atorvastatin 40-80mg will be considered equivalent to 20-40mg of Rosuvastatin. Patients on Simvastatin at the time of enrollment will be switched to Atorvastatin 40-80 mg or Rosuvastatin 20-40 mg.

After PCI of the target or culprit coronary artery (as determined by the operator) and IVUS-VH analysis of a ≥ 20 mm segment of the target coronary artery are performed during the index hospitalization for the qualifying ACS event, the patients will be randomized to ILLT or SMT if they meet all inclusion and exclusion criteria (**Figure 7, blue arrow**). PCI will be performed using standard technique at the discretion of the operator. 40-80mg daily Atorvastatin or equivalent treatments (ILLT or SMT) will be initiated within 24 hours after randomization. Patients randomized to the ILLT arm will undergo LDL-apheresis within 36 hours after presentation unless the 36-hour window is mandatory for those who were on ACE inhibitors to allow for the complete washout of ACE inhibitors. Adjunctive anti-platelet and anti-thrombin therapies will be at the discretion of the primary operator and clinical team. Refer to **Figure 8** for all study timelines.

4(c)(ii). Inclusion Criteria:

- (1). Willing and able to provide informed consent (including HIPAA)
- (2). Age > 30 years

- (3). Presenting with acute coronary syndrome (ACS), manifested as unstable angina or non-ST-elevation myocardial infarction
- (4). Referred for clinically indicated, non-emergent (the procedure is not required to be performed within 3 hours after patient presentation) coronary angiography and PCI with IVUS-VH of target coronary artery for ACS
- (5). Successful placement of two large-bore IV cannulas in bilateral upper extremities
- (6). Fasting (≥ 12 hrs) LDL ≥ 70 mg/dl while on ≤ 80 mg Atorvastatin or equivalent dose of other statin, performed at time of admission

4(c)(iii). Exclusion Criteria:

- (1). Known allergy to aspirin, statins, or iodinated contrast
- (2). Positive pregnancy test, planning to become pregnant, or breast-feeding

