4(c)(iv). Baseline Data Collection: A complete history and physical, 12-lead electrocardiogram, lipid panel, basic metabolic panel (BMP) with LFT, complete blood count, and complete cardiac catheterization, PCI, IVUS-VH and adjunctive pharmacotherapy data will be collected on all eligible patients apart from demographic and contact information.

4(c)(v). Stratification and Randomization: Prior to randomizing a patient, all screening and baseline assessments must be completed and the patient determined to be eligible for inclusion in the study. Eligible patients will be randomized to one of two treatment groups (ILLT or SMT) following an uncomplicated index PCI. 40-80mg daily Atorvastatin or equivalent statin medication treatment (ILLT or SMT) will be initiated within 24h after randomization and LDL-apheresis for ILLT group will be initiated within 36 hours of hospital admission unless the 36-hour window is mandatory for those who were on ACE inhibitors to allow for the complete washout of ACE inhibitors. Refer to **Figure 8** for all study timelines. Screening and randomization will be performed by a study coordinator, and LDL-apheresis will be conducted by a contracted specialized apheresis nurse.

4(c)(v)(1). Randomization Methods: The randomization scheme and associated codes will be developed by the Cooperative Studies Program Coordinating Center (CSPCC). Permuted block randomization with random block sizes will be employed to assign patients to either ILLT or SMT in a 1:1 ratio. The randomization will be stratified by investigation sites only.

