4(g)(ix). Sensitivity Analysis for Missing Data: In addition to the above mentioned ITT principle for primary and secondary effectiveness outcomes in which the change scores will be set to zero if the follow-up assessment is missing, other approaches will be applied in order to assess the robustness of the study results to assumptions about the missing data. For outcomes about atheroma volume and % of NC component of atheroma which will be measured only at 2 time points, the sensitivity analysis approaches include: 1) performing analysis only on complete data, 2) applying the worst case scenario (set the lowest score at baseline and the highest score at 90-day), and 3) generating imputes for missing data with multiple imputation. For outcome about EPC-CFU/ml of peripheral blood which will be repeatedly measured at four time points, the sensitivity analysis approaches include: 1) performing analysis only on complete data, and 2) using the mixed model for repeated measures.

All tests will be two-sided. The critical level for all the primary and secondary outcomes will be 0.05. No adjustments will be made for multiple secondary endpoints.

4(h) Quality Assurance, Oversight and Study Regulation

4(h)(i) Training to assure accuracy, precision and validity of the data: Toward the end of the six-month start-up period, training of study personnel will take place during a two-day kick-off meeting. All participating investigators, site research coordinators/raters, and Hines CSPCC personnel will be in attendance. Prior to the meeting, case report forms will be finalized and a detailed manual of study operations will be written and circulated. This manual will serve as the training manual for the meeting and as a reference document following the meeting. The PI's office and the data and pharmacy coordinating centers will provide the training. The general training will include the study treatment, patient screening and consent, baseline evaluation, follow-up procedures, and proper entry and maintenance of data. Cyber security awareness training and privacy training (VHA Privacy Policy, Protection of Human Research Subjects, and Good Clinical Practices) are required annually of all VA and VA-WOC employees.

4(h)(ii). Data Management and Security

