## **Handling Missing Data**

The Intent-to-treat (ITT) principle will be applied for primary and secondary effectiveness outcomes in which the change scores will be set to zero if the follow-up assessment is missing.

Other approaches will also be applied in order to assess the robustness of the study results for assumptions about the missing data. For outcomes about atheroma volume and % of NC component of atheroma which will be measured only at 2 time points, the sensitivity analysis approaches include: 1) performing analysis only on complete data, 2) applying the worst case scenario (set the lowest score at baseline and the highest score at 90-day follow-up), and 3) generating imputes for missing data with multiple imputation. For outcome about EPC-CFU/ml of peripheral blood which will be repeatedly measured at 4 time points, the sensitivity analysis approaches include: 1) performing analysis only on complete data, and 2) using the mixed model for repeated measures.

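### The worst-case sensitivity rule names no arm; applied to every patient with a missing 90-day scan, it is not a worst case for ILLT and its result follows the imbalance in missing scans

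*Protocol*

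**What the plan says.** Protocol 4(g)(ix) lists three sensitivity approaches "For outcomes about atheroma volume and % of NC component of atheroma which will be measured only at 2 time points": complete data only, a worst case, and multiple imputation. The worst case is given in one phrase, "applying the worst case scenario (set the lowest score at baseline and the highest score at 90-day". The SAP, under Handling Missing Data, repeats it: "applying the worst case scenario (set the lowest score at baseline and the highest score at 90-day follow-up". Neither text names an arm, defines the source of the lowest and highest scores, or addresses a baseline that has been observed.

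Baseline is normally known. Protocol 4(c)(v) requires that "Prior to randomizing a patient, all screening and baseline assessments must be completed". Protocol 4(c)(i) places the scan before allocation: PCI and IVUS-VH "are performed during the index hospitalization for the qualifying ACS event, the patients will be randomized to ILLT or SMT".

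The hypothesis in Protocol 4(a) is that "ILLT is superior to SMT in reducing the total atheroma volume at 90 days IVUS-VH follow up", so a rise in volume is unfavourable. The primary analysis (Protocol 4(g)(iv); SAP, Analysis of Primary Effectiveness Outcome) gives a change of zero to any patient without a 90-day measurement, in either arm.

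**The concern.** A worst case should push missing data against the hypothesis under test. For ILLT superiority, that means poor values for missing ILLT patients and good ones for missing SMT patients. A rule that gives the same very poor value to both arms does something else. With equal missingness the extreme cancels from the estimate but inflates the variance. With unequal missingness the estimate moves against whichever arm lost more scans. If SMT loses more, the analysis favours ILLT.

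The baseline half of the rule also has no clear function. Where baseline is observed, it either replaces a known value or has nothing to act on.

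This is the only one of the three sensitivity analyses that considers an extreme scenario. Complete-case analysis and standard multiple imputation do not examine whether missing patients did worse than comparable observed patients. The plan allows for 20% drop-out, so the question is a practical one.

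**Working it through.** **Inputs.** Change -0.38 (SD 2.08) for ILLT and 0.88 (SD 1.75) for SMT, 20% drop-out, N = 128 (Protocol 4(g)(ii)); 64 per arm (Protocol section 4); difference -1.26 and pooled SD 1.922 (Protocol 4(g)(vii)); two-sided 0.05 (Protocol 4(g)(ix)). These planning figures are plaque areas in mm², although the endpoint is a volume.

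**The plan's own figure.** Pooled SD = √[(2.08² + 1.75²)/2] = 1.922, and 1.26/1.922 = 0.656, which the plan gives as 0.65. At d = 0.65 the t-test needs 51 per arm (power 0.9016). Then 102/0.80 = 127.5, rounded up to 128, which reproduces the plan. The worst-case rule has no stated figure to reproduce.

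**Assumptions.** The documents give no baseline SD. One set of simulations used 2 and 4 mm² with fixed missing counts. Another set the change SD at 0.3-0.8 of the baseline SD (1.922/0.8 = 2.4 to 1.922/0.3 = 6.4 mm²). Extremes are the pooled observed ones, and missingness is unrelated to outcome. The imputed change C (highest 90-day minus lowest baseline) is then 12.5 to 22 mm², or 6.5 to 11 change SDs, in the first set and 7 to 18 SDs in the second.

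**Same rule in both arms: the estimate.** With missing fractions pI and pS:

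estimate = (1 - pI)(-0.38) - (1 - pS)(0.88) + (pI - pS)C

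*Equal missingness, true benefit.* 20% of 64 is about 13 missing and 51 observed. C cancels: (51/64)(-1.26) = -1.00, the same as under zero-change imputation. Only the variance differs. Each arm has variance of about q·s² + p·q·(C - m)², with q = 51/64 = 0.797 and p·q = 0.162. At C = 12.5:

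- ILLT: 0.797 × 4.326 + 0.162 × 12.88² ≈ 30.3
- SMT: 0.797 × 3.063 + 0.162 × 11.62² ≈ 24.3
- SE = √[(30.3 + 24.3)/63] = 0.93, so t ≈ -1.08

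Under zero change the variances are about 3.47 and 2.57, so SE = 0.31 and t ≈ -3.24. Simulated power:

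| Rule, 20% missing per arm | Missing counts | Significant for ILLT |
|---|---|---|
| Zero change | equal | 91% |
| Complete case | equal | 91% |
| Both arms, baseline replaced | equal | 0-1.3% |
| Both arms, baseline replaced | random | 6-16% |
| Both arms, baseline kept | equal | 5-29% |
| Both arms, baseline kept | random | 11-35% |

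Random counts differ because the gap in missing fractions has SD √(2 × 0.2 × 0.8/64) = 0.071. Multiplied by a C of about 12, that moves the estimate by roughly 0.9 mm² by chance, almost as much as the signal. It is also why the estimate favours SMT in 17-34% of trials with random counts.

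*Unequal missingness, no true effect (both means 0.88).* With 10% of ILLT and 30% of SMT missing (6 and 19 patients), the estimate is (6 - 19)/64 × (C - 0.88). At C = 13.1 this is -0.203 × 12.22 = -2.5; at C = 22.6 it is -0.203 × 21.72 = -4.4. False ILLT wins:

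| Rule | Fixed counts | Random counts |
|---|---|---|
| Both arms, baseline replaced | 99-100% | about 80% |
| Both arms, baseline kept | 78-88% | about 70% |
| Complete case | 2.6% | not quoted |
| Zero change | 0.4% | not quoted |

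A milder imbalance of 15% and 25%, with random counts and baseline replaced, gives false ILLT wins in 27-30%.

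**Rule for ILLT only, SMT at zero change.** With 20% missing per arm and a true benefit, the estimate is +1.5 to +3.4 against ILLT, and superiority is shown in 0% of trials.

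**The case against.** The strongest reply is that much of this is inferred from silence. A reader might infer that the plan prescribes the rule for both arms and overwrites observed baselines. It says neither. The phrase could mean ILLT patients only, or filling whichever of the two scores is missing. On the ILLT-only reading it is a severe stress test against ILLT. This stands, and it is why the finding is about an unspecified rule and its behaviour on the plain reading. Keeping the observed baseline does not rescue a two-arm rule, as the tables show.

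A second reply is that failing to confirm a real effect does not discredit an extreme bound. That also stands. An arm-specific extreme (largest observed change for missing ILLT patients, smallest for missing SMT patients) gives a mean estimate of +1.06, confirms the planning effect in 0% of trials and shows ILLT significantly worse in 54%. Low power alone therefore does not show that the planned rule is uninformative. The objection specific to it is that a two-arm version can favour ILLT when SMT loses more scans.

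Third, the percentages depend on an assumed baseline SD and on whether missing counts are equal or random. They are conditional illustrations; the pattern was the same at every SD tried.

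**Conclusion.** The concern holds in a limited form. The rule leaves open the arm, the source of the extremes and the handling of an observed baseline. On the plain reading it is not a worst case for ILLT. At 20% missing per arm it leaves about 0-16% of trials significant under the planning effect, near 0% with equal counts and 6-16% with random counts. With no true effect and 10% ILLT against 30% SMT missing, it gives a false ILLT win in roughly 80% of trials with random counts, or about 70% with observed baselines kept. If it is meant for ILLT only, it almost never confirms a real effect, as with any extreme bound.

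These sizes rest on the assumed baseline SD, the area-based planning figures, and missingness unrelated to outcome.

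A reader might go further and infer that the trial's conclusion or size is in doubt. The documents do not support that. No decision rule is attached to this analysis, and the primary zero-change test, the complete-case and multiple-imputation analyses and N = 128 are untouched. The point is worth correcting before the data are analysed, so that the choice of arm and extremes is not made once the pattern of missing scans is known.

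**What to change.** In both Protocol 4(g)(ix) and the SAP's Handling Missing Data, state that observed baselines are kept and replace item 2 with a delta-adjusted tipping-point analysis. Impute missing 90-day values with the multiple imputation already planned, worsen only the imputed ILLT values in steps, and report the shift at which significance is lost.

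Under the planning figures the answer is easy to interpret. Significance is lost when -1.26 + 0.20δ = -1.96 × 1.922 × √(2/51) = -0.746. This gives δ = 0.514/0.20, about 2.6 mm² or 1.3 change SDs. It is an approximation that ignores the extra variance from imputation. Clinical readers can judge whether such a shift is plausible, which they cannot usefully do for an imputed change of 6.5 SDs or more.

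An arm-specific extreme, unfavourable for ILLT and favourable for SMT, may be reported as an outer bound only. It should not be offered as the cure for low power, since it also fails under a real effect.

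The cost is a few lines of wording and a little programming, with no new data and no change to the sample size.
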